## 1. Study Abstract

In 2018, 12.0% of adult women in the US smoked, and approximately 7% of women continue smoking during pregnancy. Rates of smoking are even higher among women with substance use disorders. While only 16% of the US adult population reports smoking, 66% of those with a substance use disorder report smoking.

Smoking accounts for almost 3,000 stillbirths in high-income countries annually. Any smoking is associated with an 20-40% increase in the odds of stillbirth compared to not smoking, and heavy smoking (defined as ≥10 cigarettes/day) increases the odds of stillbirth by 50-80%. Maternal smoking is also associated with an increase in the risk of neonatal death, preterm birth, and low birth weight.

Unfortunately, nicotine replacement therapy has not helped women quit smoking during pregnancy. Limited data on other smoking cessation agents such as varenicline and buproprion limit their widespread use in pregnancy.

Exhaled carbon monoxide monitors, such as the Smokerlyzer® device, can be used as a motivational tool to encourage women to quit smoking. Studies in non-pregnant populations using this device to encourage smoking cessation have been promising. 12,13 The use of such monitors to measure smoking in pregnancy has also been validated and used in other studies of smoking cessation in pregnancy. 14-17 Exhaled carbon monoxide can also be directly correlated to fetal carboxyhemoglobin levels, a direct byproduct of in utero exposure to cigarette smoke.

Therefore, we propose a randomized controlled trial to evaluate the efficacy of monitoring exhaled carbon monoxide in smoking cessation during pregnancy in women with substance use disorders. We hypothesize that women who undergo exhaled carbon monoxide monitoring will have greater smoking cessation rates that those who do not undergo exhaled carbon monoxide monitoring.

## 1.1. Primary Hypothesis

Women who receive exhaled carbon monoxide (eCO) monitoring will be more likely to quit heavy smoking prior to delivery than women do not undergo eCO monitoring.

## 1.2. Secondary Hypotheses

- Women who receive eCO monitoring are more likely to quit smoking prior to delivery than women who do not receive eCO monitoring.
- Women undergoing eCO monitoring will give birth to larger infants and fewer infants that are small for gestational age.
- eCO levels at delivery will correlate to infant birth weight.
- Women undergoing eCO monitoring will give birth to infants closer to term (37 weeks gestation)
- Women using eCO monitoring will have infants with higher APGAR scores at 5 minutes
- Women undergoing eCO monitoring will be more satisfied with their prenatal care and smoking cessation experience.

## 1.3. Purpose of the Study Protocol

The purpose of this study is to determine whether eCO monitoring will aid in smoking cessation during pregnancy. This protocol describes the rationale, design, and organization of the study.

## 2. Background

## 2.1. Smoking in Pregnancy

Pregnancy is considered a time when women are highly motivated to commit to change.  Therefore, encouraging all pregnant women to quit smoking, even those with substance use disorders, can significantly improve birth outcomes. Although quitting prior to 15 weeks gestation is the most beneficial for the pregnancy, quitting prior to the third trimester improves infant birth weight. 

## 2.2. Substance Use Disorders and Smoking

Women with substance use disorders frequently also smoke. Smoking cessation is not a component of treatment for substance use disorders, and tobacco abuse is all too frequently forgotten in the face of encouraging abstinence from cocaine, heroin, and amphetamines. However, continued tobacco use is associated with relapse.  Therefore, encouraging smoking cessation during treatment for substance use disorders is essential.

## 2.3. Smoking Cessation in Pregnancy

Smoking cessation in pregnancy is recommended not only by the U.S Preventative Service Task Force (USPSTF) but also by the American College of Obstetricians and Gynecologists (ACOG). More specifically, the USPSTF recommends that all pregnant women be asked about tobacco use in pregnancy as well as offer intervention to pregnant smokers at their first prenatal visit. Such interventions that are available are using the 5A's (ask, advise, assess, assist, and arrange) as well as the [name] line.

The rate of reduction or cessation for smoking in pregnancy reduced from 18.4% to 13.2% in 1990 to 2006, respectively. Overall, when pregnant, most women are motivated to stop smoking. Of those who desire smoking cessation, 46% of prepregnancy smokers quit successfully before or during pregnancy.

The benefits of smoking cessation can improve reduction in low birth weight caused by maternal smoking as well as decrease the risks associated with maternal smoking such as placental abruption, placenta previa, preterm birth, miscarriage and stillbirth.

## 2.4. Exhaled Carbon Monoxide Monitoring

Carbon monoxide is a toxic, odorless, colorless and tasteless gas that is formed by the incomplete combustion of organic materials at high temperatures. This gas is created when smoking tobacco cigarettes and toxic as it displaces oxygen in the bloodstream to form carboxyhemoglobin (Ernst). This displacement restricts the body's tissue of oxygen leading to fatigue and other health problems. Carbon monoxide can remain in the bloodstream for up to 24 hours, has a half-life of 5 hours, and crosses the placenta causing decreased oxygenation to an unborn fetus.

The Smokerlyzer® device is one that has been used to aid in smoking cessation for non-pregnant and male patients, and now has the ability to measure not only maternal carbon monoxide levels but also record the fetal carboxyhemoglobin levels and correlate the percentage of vital oxygen that has been replaced in the bloodstream.

The device works by measuring the carbon monoxide from a 15 second inhaled breath that is blow slowly into a mouth piece until all the air in the lungs are completely exhaled. The screen then displays the maternal carbon monoxide, percent carboxyhemoglobin and percent fetal carboxyhemoglobin levels and is recorded on to the device.

## 2.5. Exhaled Carbon Monoxide Monitoring in Pregnancy

Expired carbon monoxide levels to aid in smoking cessation have been used in non-pregnant patients. A previous study conducted using a device that measured expired carbon monoxide was completed and reflected accurate smoking levels in the pregnant population. However, no study has been completed using a carbon monoxide test to promote smoking cessation in the pregnant population.

## 2.6. Rationale for a Clinical Trial

Currently, the management for smoking in pregnancy is to provide patients with resources for cessation and inform them of the risk for the fetus. Despite counseling patients, there is no way to show patients how their smoking is directly affecting their baby. Historically, it has been known that pregnant smokers overall have smaller babies. Although eCO levels can aid non-pregnant patients in smoking cessation, a randomized controlled trial is needed to determine whether measuring the maternal eCO and associated fetal carboxyhemoglobin levels in pregnancy will reduce adverse outcomes associated with smoking in pregnancy.

## 2.7. Innovation

This novel handheld device can be used in the clinic setting to provide immediate feedback for the patient and provider on smoking; this real time information can be used for biofeedback and counseling on smoking cessation.

## 3. Study Design

## 3.1. Primary Research Question

Does eCO monitoring decrease the rate of smoking ≥10 cigarettes day at the time of delivery in women with substance use disorders?

## 3.2. Secondary Research Questions

- Does eCO monitoring decrease the number of cigarettes smoked per day?
- Does eCO monitoring increase infant birth weight?
- Does maternal eCO at delivery correlate with infant birth weight?
- Does maternal eCO prior to 24 weeks correlate with infant birth weight?
- Does percent fetal carboxyhemoglobin at final measurement correlate with birth weight?
- Does eCO monitoring at delivery correlate with APGAR scores?
- Does eCO monitoring increase gestational age at delivery?
- Does eCO monitoring improve patient satisfaction with prenatal care and smoking cessation?

## 3.3. Design Summary

This is a randomized control trial. Women with a known substance use disorder who meet inclusion criteria will be offered participation in the study. Both groups will undergo eCO monitoring at enrollment, each prenatal visit and delivery. Women in the intervention group will be informed of their exhaled carbon monoxide measurement at each visit as well as the correlation to fetal carboxyhemoglobin. At each visit, women in the intervention group will receive counseling on fetal impact of smoking based on fetal carboxyhemoglobin level and institutional and state information on smoking cessation will be provided. The control group will not receive any information about their exhaled carbon monoxide or fetal carboxyhemoglobin level. At each visit, women in the control group will be provided institutional and state information on smoking cessation if they report continued smoking. Additional medications to quit smoking (nicotine replacement or other medical therapies) will not be provided to either group (although patients in either group may receive NSRIs as medically indicated for indications other than smoking cessation). The primary outcome is the number of women each group smoking ≥10 cigarettes/day at their final prenatal visit, as determined by exhaled carbon monoxide measurements. Analysis will be on an intent to treat basis.

## 3.4 Study Population and Eligibility Criteria

The study population of women with substance use disorders was selected for several reasons. First, women with substance use disorders have a significantly higher rate of smoking than women without substance use disorders. Secondly, women with substance use disorders who continue to smoke have a higher rate of relapse than those who quit smoking,  suggesting that this population will uniquely benefit from smoking cessation during pregnancy.

## a. Inclusion criteria:

- i. Age 16-45
- ii. Singleton gestation
- iii. Gestational age at enrollment <24 weeks
- iv. Substance use disorder defined as modified NIDA ASSIST ≥4

v. Cigarette smoker using ≥10 cigarettes/day interested in quitting

#### b. Exclusion criteria:

- i. Known or suspected fetal growth restriction at enrollment
- ii. Known fetal anomaly, aneuploidy, or demise
- iii. Not interested in smoking cessation or reduction during pregnancy
- iv. E-cigarette use

## 3.5 Study groups

## There will be two intervention groups:

## a. Group 1 (Standard Care treatment)

Patient exhale into Smokerlyzer® device but are blinded to maternal carbon monoxide and subsequent fetal carboxyhemoglobin levels.

## b. Group 2 (Intervention/eCO Monitoring)

Patients exhale into Smokerlyzer® device and are informed of the maternal carbon monoxide and subsequent fetal carboxyhemoglobin results. The patient will then view a chart with the levels and correspond them to the current smoking amount as well as counseled on its effects on maternal and fetal health.

#### 3.6 Informed Consent

Institutional Review Board (IRB) approved informed consent forms will be presented to the patient, and informed consent must be obtained prior to enrolling the patient in this randomized controlled trial. The full list of potential risks to the patient and her neonate will be listed in the informed consent. The nature and purpose of the study will also be detailed in the informed consent. The patient will be provided a copy of the signed informed consent. The informed consent will only be in English, and thus, only English-speaking individuals may participate in the study.

## 4. Study Procedures

## 4.1 Screening for Eligibility and Consent

All patients will be identified utilizing the IRB-approved UAB Obstetric Automated Recording (OBAR) system (IRB X030604010). This system will be used to identify patients entering prenatal care <24 weeks of pregnancy. Women will be approached at a prenatal care visit, where a member of the research team will confirm eligibility and present the study which will include the risks, benefits, procedures, and alternatives. The informed consent will be signed after all questions have been answered.

#### 4.2 Randomization

Randomization will occur after eligibility/exclusion criteria are confirmed and informed consent is obtained. Randomization will occur by a predetermined computer-generated block randomization scheme prepared by a study statistician. A variable block design will be utilized.

# 4.3 Management of patients who develop exclusion criteria (stillbirth, new fetal anomaly or aneuploidy diagnosis)

Patients that develop the exclusion criteria of stillbirth, new fetal or aneuploidy diagnosis will continue to be followed for outcomes but will be excluded from any secondary analyses that include infant outcomes.

## 4.4 Management of intervention group

At each prenatal visit, in addition to receiving standard prenatal care, women randomized to the intervention group will:

- 1) Be asked to report how many cigarettes they have smoked per day in the last week
- 2) Measure eCO
- 3) Be counseled on their exhaled carbon monoxide level and corresponding fetal carboxyhemoglobin level
- 4) Receive smoking cessation materials if reports continued smoking or eCO indicates continued smoking

## 4.5. Management of control group

At each prenatal visit, in addition to receiving standard prenatal care, women randomized to the intervention group will:

- 1) Be asked to report how many cigarettes they have smoked per day in the last week
- 2) Measure eCO
- 3) Receive smoking cessation materials if reports continued smoking

## 4.6 Adherence

Study personnel will monitor each participant at each clinic visit to conduct the exhaled carbon monoxide measurement. Study personnel will record any deviations from the protocol and adherence to the protocol will be reported in the primary manuscript.

## 4.7 Participant follow-up

Participants will be followed through discharge after delivery. At hospital admission for delivery, a final exhaled carbon monoxide measurement will be obtained. Patients will be asked to complete a survey prior to hospital discharge. Maternal and infant outcomes will be ascertained until discharge.

## 4.8 Adverse Event Reporting

As this is a low-risk study, an independent data safety monitoring board will not be formed.

We defined an adverse event as an undesirable experience or outcome occurring in a research participant, regardless of whether participation in the research study caused the event to occur. For example, placental abruption and/or stillbirth are known risks of pregnancy, and while not associated with the Smokerlyzer® device, would be considered an adverse event if it occurred during the study. All serious adverse events will be reported to the IRB. A serious adverse event will include the following events.

- a. Death
  - a. Maternal
  - b. Fetal (stillbirth)
- b. Life-threatening
- c. Prolonged hospitalization
- d. Disability or permanent damage
- e. Other serious or important medical events:
  - a. Placental abruption
  - b. Any other serious event necessitating an unanticipated higher level of care, such as a transfer to an intensive-care unit (not including anticipated transfers to neonatal ICU for prematurity, neonatal withdrawal syndrome)
- f. Any other event not listed that the investigators believe may have been caused by the intervention.

## 4.9 Study Outcome Measurements and Ascertainment

## 4.9.1. Primary outcome

Prevalence of smoking ≥10 cigarettes/day in each group at final measurement (last prenatal visit prior to delivery or at delivery), as measured by exhaled carbon monoxide

## 4.9.2. Secondary outcomes

- 1. Average number of cigarettes smoked/day in each group, as measured by exhaled carbon monoxide at final measurement
- 2. Prevalence of smoking ≥10 cigarettes/day in each group at delivery, per patient report
- 3. Average number of cigarettes smoked/day in each group, per patient report
- 4. Average exhaled carbon monoxide at final measurement
- 5. Average percent fetal carboxyhemoglobin at final measurement
- 6. Infant birthweight
- 7. APGAR at 5 minutes
- 8. Small for gestational age at birth (<10th percentile)
- 9. Gestational age at delivery

10. Patient satisfaction at final prenatal visit, measured by PANAS scales (positive and negative affect scales) and select questions on Stop Smoking Service Client Satisfaction Survey

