## 4.9.3. Follow-up and Outcome Ascertainment Periods

The primary outcome will be obtained by exhaled carbon monoxide level at the final prenatal visit, within 4 weeks of delivery. If the patient has been lost to follow up prior to delivery, every attempt will be made to obtain an exhaled carbon monoxide level at admission for delivery. Patient satisfaction will also be assessed at the final measurement. Each patient will be asked about number of cigarettes smoked per day for the last week at each prenatal visit. Delivery outcomes will be assessed prior to discharge.

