## Positive and Negative Affect Schedule (PANAS-SF)

Indicate the extent you have felt this way over the past week		Very slightly or not at all	A little	Moderately	Quite a bit	Extremely
PANAS 1	Interested			3	0 4	
PANAS 2	Distressed	 		 3	0 4	
PANAS 3	Excited	 		3	0 4	
PANAS 4	Upset	 		3	0 4	
PANAS 5	Strong			3	4	
PANAS 6	Guilty	 		 3	4	
PANAS 7	Scared			3	4	
PANAS 8	Hostile			3	4	
PANAS 9	Enthusiastic			3	4	
PANAS 10	Proud			3	4	
PANAS 11	Irritable	 		 3	4	
PANAS 12	Alert	 		3	4	
PANAS 13	Ashamed			3	4	
PANAS 14	Inspired			3	4	
PANAS 15	Nervous			3	4	
PANAS 16	Determined			3	4	
PANAS 17	Attentive			 3	4	

PANAS	Jittery	 		3	4	
18						
PANAS	Active		2	○ 3	4	 
19						
PANAS	Afraid		2	○ 3	4	 
20						

8.	6 Patient Survey									
	Smoking Reduction I	n Gr	avid Wom	nen wi	th Substar	ice Us	se Disord	ders (S	IGS):	
		ΑΙ			ntrolled Tr	ial				
				ent Sur	vey*					
_	lame:	MR					Study I			
	e final part of your participation in	n the	e research	study	is to comp	olete 1	this shor	t surve	ey. This sho	ould ta
a t	total of 15 minutes of your time.									
Ρle	ease circle the appropriate number	r for	each ques	stion:						
1.	Overall, how satisfied are you wit	th th	e support	you h	ave receiv	ed to	stop sm	oking?	)	
	Van Uncatisfied Una	satis	fied	lnaura		atisfi	ad	1/05	Catisfied	
	Very Unsatisfied Uns 1	satis 2	nea c	Jnsure 3	: 3	4	eu	very	Satisfied 5	
	1	۷		5		7			3	
2.	Would you recommend using the	e car	bon mond	oxide r	eading dev	vice (S	Smokerly	yzer) to	o other sm	okers
	who a want to stop smoking?									
								No	Unsure	Yes
								1	2	3
3.	In the event that you started sm	okin	ng again w	ould v	ou use the	Smo	kerlyzer	device	e to help w	ith
	stopping smoking?		.0 -0	,			,			
								No	Unsure	Yes
								1	2	3

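### The exploratory satisfaction outcome pairs a past-week mood scale with a cessation-service survey; neither asks directly about prenatal care, and the time of collection conflicts between sections.

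*Combined protocol and SAP*

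**What the plan says.** **The hypothesis and the question.** Section 1.2 predicts: "Women undergoing eCO monitoring will be more satisfied with their prenatal care and smoking cessation experience". Section 3.2 asks: "Does eCO monitoring improve patient satisfaction with prenatal care and smoking cessation". Both name two objects of satisfaction: prenatal care and smoking cessation.

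**The measure.** Section 4.9.2, item 10, reads "Patient satisfaction at final prenatal visit, measured by PANAS scales (positive and negative affect scales" and continues "and select questions on Stop Smoking Service Client Satisfaction Survey". There are thus two instruments. The PANAS form is in Appendix 8.5 and the survey is in Appendix 8.6. The PANAS instruction is "Indicate the extent you have felt this way over the past week".

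**The time.** Item 10 sets the final prenatal visit. Section 4.9.3 says "Patient satisfaction will also be assessed at the final measurement", and 4.9.1 describes that occasion as "at final measurement (last prenatal visit prior to delivery or at delivery". Section 4.7 says "Patients will be asked to complete a survey prior to hospital discharge".

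**The status.** Section 5.2 calls the satisfaction analysis exploratory, and there describes it as satisfaction with the device.

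**The concern.** An outcome should measure what its hypothesis names. Here one of the two instruments measures mood. The intervention tells a woman her reading and counsels her on its effect on the fetus (3.3, 3.5, 4.4). Such feedback could plausibly move guilt or distress without moving satisfaction, or move the two in opposite directions. If a PANAS difference is reported under the satisfaction label that 4.9.2 gives it, readers may draw the wrong conclusion about how women received the intervention.

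The second instrument does measure satisfaction, but with the help given to stop smoking. If no item asks about prenatal care, the first half of the hypothesis in 1.2 cannot be tested directly, whatever the sample size. An item that was never asked cannot be recovered at analysis.

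Timing matters for the same reason. If staff follow different sections, women may answer at different stages, and the answers will not refer to the same period.

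**Working it through.** The documents give no effect size, standard deviation or power for satisfaction, so there is no figure to reproduce. The check compares what the hypothesis names with what the forms ask, and then compares the timing statements.

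**Step 1: PANAS (8.5).** The form lists 20 words, among them Interested, Distressed, Guilty, Proud, Ashamed and Determined, each rated for the past week. Words about care, support, staff or service: 0 of 20. The form yields affect.

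**Step 2: the survey (8.6).** Its nine items, by subject:

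| Item | Subject | Response |
|---|---|---|
| 1 | Overall satisfaction with help to stop smoking | 1-5 |
| 2 | Recommending the device to others | No/Unsure/Yes |
| 3 | Using the device after a relapse | No/Unsure/Yes |
| 4 | Joining the study again | No/Unsure/Yes |
| 5 | Smoking since the last appointment | No/Unsure/Yes |
| 6 | Satisfaction with the staff | 1-5 |
| 7 | Information and advice at appointments | 1-5 |
| 8 | Helpfulness of written information | No/Unsure/Yes |
| 9 | Helpfulness of the CO reading | No/Unsure/Yes |

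Items 1, 6, 7 and 8 bear on the support received. Items 2, 3 and 9 concern the device or its reading. They are hard to compare between arms, because women in Group 1 are not shown their results (3.5). Items 4 and 5 do not measure satisfaction with care. Items asking directly about satisfaction with prenatal care: 0 of 9. Item 7 comes nearest, but only indirectly.

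**Step 3: match to the hypothesis.**

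- Smoking cessation experience: measured by items 1, 6, 7 and 8.
- Prenatal care: 0 of 20 + 9 = 29 items ask about it directly.
- The device, which is the target named in 5.2: items 2, 3 and 9. Neither 1.2 nor 3.2 names this target.

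**Step 4: timing.**

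- 4.9.2, item 10: final prenatal visit.
- 4.9.3: final measurement. Under 4.9.1 this can be the last prenatal visit or delivery, so it is compatible with item 10. Section 4.9.3 places the final prenatal visit within 4 weeks of delivery and seeks a reading at delivery admission for women lost to follow-up.
- 4.7: a survey before hospital discharge, hence at the end of the delivery stay. The form in 8.6 introduces itself as the last part of participation, which fits this time better than a prenatal visit.

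The first two statements can be read together. The third cannot be read as the same occasion if the survey it refers to is the one named in item 10. Section 4.7 does not say which instrument it means.

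**The case against.** The strongest defence has four parts.

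1. **Two instruments are named.** A reader who stops at the PANAS wording might infer that satisfaction is defined by a mood scale alone. The same sentence adds the satisfaction survey, and its items 1, 6, 7 and 8 cover the cessation half of the hypothesis. This stands: the plan can address satisfaction with cessation support. It does not make the PANAS score a measure of satisfaction.

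2. **Study contacts take place at prenatal visits.** Items 6 and 7, on staff and on advice at appointments, therefore touch prenatal care. This stands in part. They are indirect, and the form opens with support to stop smoking, so an answer cannot be read as a rating of prenatal care.

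3. **The timing conflict is smaller than it looks.** A reader might count three different times, or infer that PANAS is completed after delivery so that its one-week recall takes in the birth. The documents support neither reading. The final prenatal visit and the final measurement are compatible. Section 4.7 mentions only a survey, 8.5 and 8.6 are separate forms, and no section puts PANAS after delivery. Nor does anything suggest that timing would differ by arm. What remains is one conflict: prenatal visit or final measurement against pre-discharge.

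4. **The outcome is tenth of ten secondary outcomes and is exploratory.** This stands and limits the consequence. The label does not change what a form measures.

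**Conclusion.** The point holds in a limited form. PANAS measures past-week affect and should not carry the satisfaction label. The survey covers satisfaction with cessation support. No item in either instrument asks directly about satisfaction with prenatal care, so half of the hypothesis in 1.2 and 3.2 lacks a direct measure. There is one clear timing conflict, between 4.9.2 with 4.9.3 and 4.7.

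A reader might go further and infer that the trial can say nothing about satisfaction. That is not supported, because the cessation half is measured.

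The size is small. It is a count of items (0 of 29 on prenatal care), not a bias in any estimate, and the primary outcome, sample size and safety reporting are untouched. The documents define no composite score and do not say how PANAS will be reported. The risk of a mood difference being presented as satisfaction therefore comes from the label in item 10, not from a stated analysis. Movement in guilt or distress is a possibility for which the documents give no figure.

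The conclusion assumes that the forms printed in 8.5 and 8.6 are the ones to be used.

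**What to change.** 1. **In 4.9.2, item 10:** take satisfaction from the survey's satisfaction items and name the items used. Item 1 (overall, 1-5) is one reasonable choice, but the documents do not require a single item. List the PANAS positive and negative scores separately, as affect.
2. **Prenatal care:** either add one 1-5 item on satisfaction with prenatal care to the survey in 8.6, or remove prenatal care from the hypothesis in 1.2 and the question in 3.2.
3. **Timing:** state one time point for each instrument, the same in both arms, and use it consistently in 4.7, 4.9.2 and 4.9.3. The two instruments need not share a time point, but each needs only one.

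The cost is rewording in a few sections and at most one extra survey question. The primary outcome and its sample size do not change. The new item and the time points need to be in place before responses are collected, since neither can be repaired afterwards.
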